3.1.4 Per Protocol Set (PPS)

The PPS will consist of all randomized patients who have an efficacy evaluation (number of hours per day spent in the OFF state while awake) at Week 24 and have no major protocol deviations/violations. In addition, subjects randomized to tozadenant must have measureable plasma concentrations at each post-baseline visit for the subject to be considered in the PPS (i.e. not have any below-the-limit-of-quantification result from the bioanalysis at any post-baseline visit). This will not exclude subjects who had missing samples or values, for any reason, from the analysis. (For example, instances where the analytical lab was unable to obtain a result from a sample they received, or no sample was received, or the bioanalytical results were considered invalid.)

Patients will be accounted for in the treatment group to which they were originally randomized.

Summaries and/or analyses of the primary endpoint and four key secondary endpoints will be done in the PPS.

3.2 Sample Size Considerations

The primary efficacy endpoint is the change from Baseline to Week 24 in the number of hours per day spent in the OFF state. A sample size of 150 in each group will provide 85% power to detect a difference in mean response of 0.9 hours between tozadenant and placebo assuming the common SD is 2.6 hours and using a two group t-test with a 0.050 two-sided significance level. Across the 3 treatment groups, the total number of patients to be randomized is 450.

Although the sample size calculation is based on the primary endpoint, OFF time, for this study the total sample size of 450 patients is anticipated to yield power to detect treatment differences

in the two key secondary endpoints as summarized in the table below. The assumed treatment differences and standard deviations are based on the findings of the SYN115-CL02 study.

CONFIDENTIAL

Estimated Power for Key Secondary Efficacy Endpoints

Secondary Endpoint	SYN11	Power	
120 mg BID vs. placebo	Treatment	Standard	
	Difference	Deviation	
Good ON time: Number of hours spent in the	1.19	2.64	97%
ON state without troublesome dyskinesia			
UPDRS Parts II + III total score	3.00	8.38	87%

Approximately 645 patients will be screened, assuming a 30% screen failure rate, to randomize 450 patients.

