11.4.3 Multiplicity Adjustment for Primary and Key Secondary Endpoints

All analyses of the primary and two key secondary endpoints will focus on the comparison of tozadenant 120 mg BID vs. placebo followed by tozadenant 60 mg BID vs. placebo. The following six comparisons will be conducted using sequential testing with a fixed sequence, which controls the family-wise error for multiple comparisons at an alpha level of 0.05 (two-tailed):

- 1. Comparison of tozadenant 120 mg BID vs. placebo using the primary endpoint (Change from baseline to Week 24 in the number of hours per day spent in OFF state).
- 2. Comparison of tozadenant 120 mg BID vs. placebo using the first key secondary endpoint (Change from baseline to Week 24 in the number of hours per day spent in good ON time, defined as the sum of ON time without dyskinesia and ON time with non-troublesome dyskinesia).
- 3. Comparison of tozadenant 120 mg BID vs. placebo using the second key secondary endpoint (Change from baseline to Week 24 in UPDRS Parts II + III total score).
- 4. Comparison of tozadenant 60 mg BID vs. placebo using the primary endpoint (Change from baseline to Week 24 in the number of hours per day spent in OFF state).
- 5. Comparison of tozadenant 60 mg BID vs. placebo using the first key secondary endpoint (Change from baseline to Week 24 in the number of hours per day spent in good ON time, defined as the sum of ON time without dyskinesia and ON time with non-troublesome dyskinesia).
- 6. Comparison of tozadenant 60 mg BID vs. placebo using the second key secondary endpoint (Change from baseline to Week 24 in UPDRS Parts II + III total score).

Testing will begin with tozadenant 120 mg BID vs. placebo for change from baseline to Week 24 in the number of hours per day spent in OFF state. If the p-value is less than or equal to an $\alpha = 0.05$, then the result is considered statistically significant and testing will proceed to the next comparison, and so forth. Testing will stop with the first adjusted p-value >0.05 and that comparison, as well as any comparison later in the sequence will be considered not statistically significant.

The adjusted p-values p'_i for i = 1 to 6 will be calculated by taking the maximum of the raw p-value (p_i) from the statistical test and the adjusted p-value (p_{i-1}) from the prior test, as shown below:

P-values from the analyses of all other efficacy outcomes will be reported as nominal, with no adjustment for multiplicity.

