9.6.6 Adjustment for Multiplicity

9.6.6.1 Tozadenant 120 mg BID vs. Placebo and tozadenant 60 mg BID vs. Placebo

All analyses of the primary and two key secondary endpoints will focus on the comparison of tozadenant 120 mg BID vs. placebo followed by tozadenant 60 mg BID vs. placebo. The following six comparisons will be conducted using sequential testing with a fixed sequence, which controls the family-wise error for multiple comparisons at an alpha level of 0.05 (two-tailed):

- 1. Comparison of tozadenant 120 mg BID vs. placebo using the primary endpoint (change from baseline to Week 24 in the number of hours per day spent in OFF state).
- 2. Comparison of tozadenant 120 mg BID vs. placebo using the first key secondary endpoint (Change from baseline to Week 24 in the number of hours per day spent in good ON time, defined as the sum of ON time without dyskinesia and ON time with non-troublesome dyskinesia).
- 3. Comparison of tozadenant 120 mg BID vs. placebo using the second key secondary endpoint (Change from baseline to Week 24 in UPDRS Parts II + III total score).

4. Comparison of tozadenant 60 mg BID vs. placebo using the primary endpoint (change from baseline to Week 24 in the number of hours per day spent in OFF state).

CONFIDENTIAL

- 5. Comparison of tozadenant 60 mg BID vs. placebo using the first key secondary endpoint (Change from baseline to Week 24 in the number of hours per day spent in good ON time, defined as the sum of ON time without dyskinesia and ON time with non-troublesome dyskinesia).
- 6. Comparison of tozadenant 60 mg BID vs. placebo using the second key secondary endpoint (Change from baseline to Week 24 in UPDRS Parts II + III total score).

Testing will begin with tozadenant 120 mg BID vs. placebo for change from baseline to Week 24 in the number of hours per day spent in OFF state. If the p-value is less than or equal to an α =0.05, then the result is considered statistically significant and testing will proceed to the next comparison, and so forth. Testing will stop with the first adjusted p-value > 0.05 and that comparison, as well as any comparison later in the sequence will be considered not statistically significant.

The adjusted p-values p'_i for i=1 to 6 will be calculated by taking the maximum of the raw p-value (p_i) from the statistical test and the adjusted p-value (p'_{i-1}) from the prior test, as shown below:

```
\dot{p}_1 = p_1 

\dot{p}_2 = \max(\dot{p}_1, p_2) 

\dot{p}_3 = \max(\dot{p}_2, p_3) 

... 

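### The 97% and 87% power printed in SAP 3.2 for the 120 mg key secondaries are stand-alone figures; under the plan's fixed testing sequence and its own OFF-time assumption, both are at most 85%

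*SAP*

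**What the plan says.** SAP 3.2 sizes the trial on OFF time: "A sample size of 150 in each group will provide 85% power". The stated aim is to "detect a difference in mean response of 0.9 hours between tozadenant and placebo", and the assumptions read "common SD is 2.6 hours and using a two group t-test with a 0.050 two-sided significance level". For the key secondaries, the claim is that "the total sample size of 450 patients is anticipated to yield power to detect treatment differences". It is backed by a table headed "Estimated Power for Key Secondary Efficacy Endpoints", for 120 mg BID vs placebo:

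- good ON time: difference 1.19 h, SD 2.64 h, power 97%
- UPDRS Parts II+III: difference 3.00, SD 8.38, power 87%

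On the source of these inputs the SAP says: "The assumed treatment differences and standard deviations are based on the findings of the SYN115-CL02 study". The section does not mention the order of testing.

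The testing rule is in Protocol 11.4.3, "The following six comparisons will be conducted using sequential testing with a fixed sequence", and is repeated in SAP 9.6.6. The first three tests are all 120 mg vs placebo: OFF time, then good ON time, then UPDRS II+III. The SAP's stopping rule begins "Testing will stop with the first adjusted p-value > 0.05 and that comparison, as well as any comparison later in the sequence will be considered", and it ends by calling all of these non-significant. Each adjusted p-value is the larger of that test's raw p-value and the preceding adjusted p-value, so the gate is built into the reported result.

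**The concern.** Protocol 2.2.2 presents the key secondaries as endpoints tested within a prespecified hierarchy. A reader of SAP 3.2 will therefore tend to take the tabulated power as the chance that each endpoint is declared significant under that hierarchy. It is not. An endpoint in position 2 or 3 cannot be claimed unless every earlier test succeeds, so its chance of a claim cannot exceed the power of the first test.

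The table makes good ON time look almost certain and UPDRS II+III (87%) better placed than the primary (85%), although UPDRS II+III needs OFF time and good ON time to succeed first. These are confirmatory claims, and the SAP introduction says the document was written to support a Special Protocol Assessment. What is at stake is how the trial's prospects are described. The validity of the tests and the error rate are not in question.

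**Working it through.** **Inputs (SAP 3.2).** n = 150 per arm, two-sided 5% two-group t-test, so df = 298 and the critical value is 1.968. OFF time 0.9 h / SD 2.6; good ON time 1.19 h / SD 2.64; UPDRS II+III 3.00 / SD 8.38. No missing data is assumed, as in the printed figures. Correlations between endpoints are not in the documents; the values below are assumptions, signed so that positive means benefit on both.

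**Step 1: reproduce the printed powers.** Noncentrality = difference / (SD × √(2/150)), with √(2/150) = 0.1155.

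- OFF: 0.9 / 0.3002 = 2.998, power 84.8% (normal approximation 85.0%); printed 85%.
- Good ON: 1.19 / 0.3048 = 3.904, power 97.3% (97.4%); printed 97%.
- UPDRS II+III: 3.00 / 0.9676 = 3.100, power 87.1% (87.3%); printed 87%.

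All three reproduce as single tests with no gate.

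**Step 2: bounds under the sequence, with no correlation assumption.** The chance that all of a set of tests succeed is at most the smallest single power, and at least the sum of the powers minus (number of tests − 1).

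- Good ON (tests 1 and 2): at most 84.8%; at least 0.848 + 0.973 − 1 = 0.821. Range 82–85%.
- UPDRS II+III (tests 1, 2 and 3): at most 84.8%; at least 0.848 + 0.973 + 0.871 − 2 = 0.692. Range 69–85%.

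The best case is therefore 12 points below the printed 97% and 2 points below the printed 87%.

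**Step 3: values under assumed correlations.** The test statistics are taken as multivariate normal with the three stand-alone powers (normal approximation) as margins. Noncentral t margins lower the entries by up to about 0.4 points.

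| OFF / good ON correlation | Good ON claimable | UPDRS II+III claimable, UPDRS correlation with both diary endpoints 0 | 0.4 | 0.6 | 0.8 |
|---|---|---|---|---|---|
| 0 | 82.8% | 72.3% | 75.2% | 77.3% | not possible |
| 0.5 | 83.9% | 73.2% | 75.9% | 77.7% | 80.2% |
| 0.8 | 84.8% | 74.0% | 76.5% | 78.2% | 80.4% |
| 0.9 | 85.0% | 74.2% | 76.6% | 78.3% | 80.5% |

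The independent case can be checked by hand: 0.850 × 0.974 = 0.828, and 0.828 × 0.873 = 0.723. OFF and good ON time come from the same diary, so the lower rows are the more plausible ones for that pair.

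**Step 4: sensitivity to the OFF-time effect.** With SD 2.6 and other inputs unchanged, an assumed OFF effect of 1.0 h gives noncentrality 1.0 / 0.3002 = 3.331 and OFF power of about 91%. Good ON then becomes 89–91%. UPDRS II+III becomes about 78–84% for UPDRS correlations of 0 to 0.8 (independent case 0.915 × 0.974 × 0.873 = 0.778). At an assumed 1.19 h, OFF power is 97.7% and good ON is 95–97%.

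**The case against.** The strongest reply is that nothing has been miscalculated. The table gives per-endpoint power, and 97% and 87% are right for that quantity. This stands: a reader might infer an arithmetic error, and there is none. SAP 3.2 never says the figures are probabilities of success under the sequence. The gap is that it does not say they ignore the sequence either.

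Second, the 85% ceiling holds only if the OFF effect is the planning value. SAP 3.2 gives 0.9 h without naming a dose, while the secondary inputs are 120 mg estimates from SYN115-CL02. The documents do not give that study's OFF-time effect. This also stands. A reader might infer that the rule caps good ON time at 85% in all circumstances, but Step 4 shows the ceiling moves with the OFF assumption. In addition, the tests in the sequence come from a baseline-adjusted MMRM (SAP 9.6.1), so a t-test power of 85% is itself a planning approximation.

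Third, a single figure for UPDRS II+III depends on correlations nobody has stated. A reader might infer a flat one-in-four chance that it fails. The supported statement is 22–28% for UPDRS correlations of 0 to 0.6, about 20% at 0.8, and 15–31% with no correlation assumption, all conditional on the 0.9 h value. The printed 87% implies 13%.

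Fourth, SAP 3.2 bases the sample size on the primary endpoint alone, so no design decision rests on this table. That is correct and limits the weight of the point. It also cannot be said that the SAP table is the only support for the secondary claims. The protocol's list of tables names a power table for the key secondaries (Table 5) that is not visible in the public text of Protocol 11.10, and the SAP refers to a Special Protocol Assessment document that is not available here.

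**Conclusion.** The point holds as a matter of what the printed figures mean. The 97% and 87% are correct stand-alone powers, but they are not the chance of a claimable result under SAP 9.6.6 and Protocol 11.4.3.

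On the SAP's own inputs, with 150 per arm and no missing data, the sequence-based figures are:

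- good ON time 82–85%, which is 12–15 points below the printed value;
- UPDRS II+III 69–85%, which is 2–18 points below. For assumed correlations with the diary endpoints of 0 to 0.6 it is about 72–78%, or 9–15 points below.

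The ranges 82–85% and 69–85% need no correlation assumption. All the figures rest on the 0.9 h / SD 2.6 h OFF-time assumption, and a larger OFF effect would raise them. The point does not show that the trial is too small or that the multiplicity procedure is faulty. It leaves aside dropout and the 60 mg comparisons. The plan should be corrected, but the correction is to reporting only.

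**What to change.** In the SAP 3.2 table:

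1. Label the 97% and 87% column *stand-alone, ignoring the testing sequence*.
2. Add a column for power under the sequence: good ON time 82–85%; UPDRS II+III 72–78% for assumed correlations with the diary endpoints of 0 to 0.6, with correlation-free bounds of 69–85%.
3. Add a sentence saying that these values are conditional on the 0.9 h / 2.6 h OFF-time assumption and that a larger OFF effect would raise them. For example, an assumed 1.0 h gives about 89–91% for good ON time and 78–84% for UPDRS II+III. If the sponsor has endpoint correlations from SYN115-CL02, use those and state them.

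Make the same change in the protocol's power table if it carries the same figures.

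The cost is a few cells, one or two sentences and a short calculation. The stated figures become less favourable. Sample size, alpha, testing order and analysis do not change.

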3.3 Randomization

During Part A, an IXRS will be used for assigning eligible patients to a treatment regimen based on a predetermined randomization schedule. The final randomization schedule will be created and sent to the IXRS provider. The IXRS is responsible for assigning blinded IMP kits to randomized patients, as appropriate, according to the randomization and the visit schedule. Patients will be randomly allocated in equal proportion (1:1:1) to 1 of 3 double-blind treatment groups:

- Group A: tozadenant 60 mg BID (one 60 mg active tozadenant tablet plus one placebo tablet, BID)
- Group B: tozadenant 120 mg BID (two 60 mg active tozadenant tablets, BID)
- Group C: placebo BID (two placebo tablets, BID)

4 STUDY VARIABLES AND COVARIATES

4.1 Primary Efficacy Endpoint (Part A)

The primary efficacy endpoint will be the change from Baseline to Week 24 in the number of hours per day spent in the OFF state, as assessed by patient-completed PD diaries and averaged over 3 consecutive days.

A valid diary (see **Section 5.3**) will not have more than 2 hours (4 invalid entries) over a given 24-hour period. An invalid diary entry is defined as more than one entry recorded in a given half hour interval, an unreadable entry, or the absence of an entry in a given half hour interval. The average diary information from 3 valid diaries (if available) for each visit will be used to calculate diary-based efficacy endpoints. If there are only 2 valid diaries for a visit then the average information from the 2 valid diaries will be used. If only one diary is valid, information from the single valid diary will be used. If no valid diaries are available for a patient visit then the diary information is considered missing.

4.2 Secondary Endpoints

4.2.1 Key Secondary Efficacy (Part A)

Key secondary efficacy endpoints include:

- 1. Change from Baseline to Week 24 in number of hours per day spent in good ON time, defined as the sum of ON time without dyskinesia and ON time with non-troublesome dyskinesia.
- 2. Change from Baseline to Week 24 on UPDRS Parts II (ADL subscale) + III (motor subscale) total scores.

4.2.2 Other Secondary Efficacy (Part A)

The other secondary efficacy endpoints include the change from Baseline to Week 24 (where applicable), for the following:

- 1. CGI-I at Week 24.
- 2. PGI-I at Week 24.
- 3. UPDRS Part III (motor subscale) score in the ON state.
- 4. CGI-S.
- 5. UPDRS Part II (ADL subscale) score.
- 6. Number of hours per day spent in the ON state (without dyskinesia, with non-troublesome dyskinesia, or with troublesome dyskinesia).
- 7. Number of hours per day spent in the ON state without dyskinesia.
- 8. Number of hours per day spent in the ON state with any dyskinesia (troublesome or non-troublesome).
- 9. Number of hours per day spent in the ON state with non-troublesome dyskinesia.
- 10. PDQ 39 (total score and individual domain scores).
- 11. UPDRS Part IV score.
- 12. UPDRS Part I score.

4.2.3 Exploratory (Part A)

The exploratory endpoints in Part A include the change from Baseline to Week 24 (where applicable), for the following:

- 1. Number of hours per day spent in the asleep state.
- 2. Dyskinesia as measured by questions 32, 33 and 34 of UPDRS Part IV.
- 3. Falls as measured by question 13 on UPDRS Part II.
- 4. Responder analysis of number (%) of patients with ≥ 1.0 h improvement in OFF time (evaluated at Week 24).
- 5. Responder analysis of number (%) of patients with ≥ 2.0 h improvement in OFF time (evaluated at Week 24).
- 6. Percent change in total levodopa equivalent dose.

- 7. Percent change in the number of hours per day spent in OFF state.
- 8. Percent change in the number of hours per day spent in ON state without troublesome dyskinesia.

CONFIDENTIAL

- 9. Percent change in the number of hours per day spent in ON state with troublesome dyskinesia.
- 10. Scales for Outcomes in Parkinson's Disease-cognition (SCOPA-cog) score.
- 11. Fall questionnaire score.
- 12. Number of hours per day spent in the OFF state in the sub-population of subjects taking levodopa and only one additional concomitant anti-PD medication.
- 13. Number of hours per day spent in the OFF state in the sub-population of subjects taking levodopa and two additional concomitant anti-PD medications.
- 14. Number of hours per day spent in the OFF state in the sub-population of subjects taking levodopa and three additional concomitant anti-PD medications.
- 15. EuroQol 5D-5L Health Questionnaire (EQ-5D-5L).
- 16. Treatment Satisfaction Questionnaire for Medication (TSQM 9) (evaluated at Week 76).

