7.7 Treatment Satisfaction Questionnaire for Medication (TSQM-9)

The TSQM-9 is a 9-item validated questionnaire that assesses patients' satisfaction with medication and captures information on treatment effectiveness, convenience, and global satisfaction (Bharmal, 2009; Atkinson et al, 2004; Atkinson et al, 2005). The TSQM-9

provides 4 domain scores: effectiveness, convenience, and global satisfaction ranging from 0 to 100 with higher scores representing higher satisfaction on that domain.

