11.4.5 Exploratory Analyses (Part A)

The exploratory analyses in Part A include the change from Baseline to Week 24, for the following:

- 1. Number of hours per day spent in the asleep state.
- 2. Dyskinesia as measured by questions 32, 33 and 34 of UPDRS Part IV.
- 3. Falls as measured by question 13 on UPDRS Part II.
- 4. Responder analysis of number (%) of patients with ≥ 1.0 h improvement in OFF time (evaluated at Week 24).
- 5. Responder analysis of number (%) of patients with \geq 2.0 h improvement in OFF time (evaluated at Week 24).
- 6. Percent change in total levodopa equivalent dose.

- 7. Percent change in the number of hours per day spent in OFF state.
- 8. Percent change in the number of hours per day spent in ON state without troublesome dyskinesia.
- 9. Percent change in the number of hours per day spent in ON state with troublesome dyskinesia.
- 10. Scales for Outcomes in Parkinson's Disease–cognition (SCOPA-cog) score.
- 11. Fall questionnaire score.
- 12. Number of hours per day spent in the OFF state in the sub-population of subjects taking levodopa and only one additional concomitant anti-PD medication.
- 13. Number of hours per day spent in the OFF state in the sub-population of subjects taking levodopa and two additional concomitant anti-PD medications.
- 14. Number of hours per day spent in the OFF state in the sub-population of subjects taking levodopa and three additional concomitant anti-PD medications.
- 15. EQ-5D-5L.
- 16. TSQM-9 (evaluated at Weeks 6 and 24).

These analyses will be documented by descriptive statistics by treatment group in the mITT. No statistical analyses are planned.

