11.5.2 Other Analyses

Patient Disposition

The number of patients who were screened, randomized, completed scheduled follow up, and prematurely withdrew study participation will be summarized overall and by treatment group. Reasons for non-participation and for withdrawal from study will also be presented.

Exposure to IMP/Compliance

The number of days of exposure to IMP will be summarized by treatment group. Compliance with IMP will be calculated as the number of doses taken divided by the scheduled number of doses taken, expressed as a percentage. Compliance will be summarized overall and by week for each treatment group.

Prior and Concomitant Medication Use

All prior and concomitant medications taken during the study period will be listed for each patient, including dosage and indication. Medications will be coded using the World Health Organization (WHO) Drug Dictionary Enhanced and classified as past medication (last dose taken prior to the first dose of IMP), concomitant medication ongoing at Baseline, or concomitant medication initiated after Baseline. The percentage of patients taking each medication (or class of medications) will be summarized overall and by treatment group.

Plasma Drug Concentrations

Results of the assays of tozadenant (and of pramipexole, in patients concomitantly taking pramipexole during the study) will be descriptively analyzed and reported in the clinical study report. Separate population analysis on the data from this study alone or combined with data from other studies as deemed appropriate will be performed and reported separately.

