1 INTRODUCTION

TOZ-CL05 will include a 24-week double-blind phase (Part A) followed by a 52-week open-label phase (Part B). This statistical analysis plan (SAP) describes the statistical methods to be used during the reporting and analyses of data collected under Part A (double-blind phase) of Biotie's Protocol TOZ-CL05. The SAP for Part B (open-label phase) will be submitted at a later date. The SAP was developed to support Biotie's Special Protocol Assessment (SPA).

This SAP should be read in conjunction with the study protocol and the SPA document. This version of the plan has been developed using final protocol Amendment No. 1, dated 19 May 2015.

Table, figure and listing (TFL) shells will be developed at a later date.

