9.3 Treatments

9.3.1 Extent of Study Drug Exposure

The number of days of exposure to study drug will be summarized by treatment group in the SS. Descriptive statistics (n, mean, standard deviation, median, minimum, and maximum) for the total number of tablets taken, number of tablets returned and number of tablets lost will be displayed. Compliance with study drug will be calculated as the number of doses taken divided by the scheduled number of doses taken, expressed as a percentage. Compliance will be summarized overall and by scheduled weeks (Week 2, 6, 18 and 24) for each treatment group for the safety analysis set. The reason for not returning tablets is captured on the CRF and will be presented in the data listings.

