9.6.5 Exploratory Variables

The exploratory variables will be summarized by descriptive statistics by treatment group in the mITT. No statistical analyses are planned. The list of variables includes the change from Baseline to Week 24 (where applicable) for the following:

- 1. Number of hours per day spent in the asleep state.
- 2. Dyskinesia as measured by questions 32, 33 and 34 of UPDRS Part IV.
- 3. Falls as measured by question 13 on UPDRS Part II.
- 4. Responder analysis of number (%) of patients with ≥ 1.0 h improvement in OFF time (evaluated at Week 24).
- 5. Responder analysis of number (%) of patients with ≥ 2.0 h improvement in OFF time (evaluated at Week 24).
- 6. Percent change in total levodopa equivalent dose.
- 7. Percent change in the number of hours per day spent in OFF state.
- 8. Percent change in the number of hours per day spent in ON state without troublesome dyskinesia.
- 9. Percent change in the number of hours per day spent in ON state with troublesome dyskinesia.
- 10. Scales for Outcomes in Parkinson's Disease-cognition (SCOPA-cog) score.
- 11. Fall questionnaire score.
- 12. Number of hours per day spent in the OFF state in the sub-population of subjects taking levodopa and only one additional concomitant anti-PD medication.
- 13. Number of hours per day spent in the OFF state in the sub-population of subjects taking levodopa and two additional concomitant anti-PD medications.
- 14. Number of hours per day spent in the OFF state in the sub-population of subjects taking levodopa and three additional concomitant anti-PD medications.

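### The Part A SAP times TSQM-9 at Week 76, leaves TSQM-9 and EQ-5D-5L off its list of exploratory summaries, and skips Week 12 for compliance; only descriptive outputs are affected.

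*SAP*

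**What the plan says.** **Scope.** SAP section 1 states: "TOZ-CL05 will include a 24-week double-blind phase (Part A) followed by a 52-week open-label phase (Part B"). It confines the document to Part A and adds: "The SAP for Part B (open-label phase) will be submitted at a later date".

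**TSQM-9 timing.** SAP 4.2.3, the Part A exploratory list, has 16 items. Item 15 is EQ-5D-5L and item 16 is "Treatment Satisfaction Questionnaire for Medication (TSQM 9) (evaluated at Week 76"). For the same Part A item, protocol 11.4.5 has "TSQM-9 (evaluated at Weeks 6 and 24"), and protocol 2.2.4 gives the same two weeks. In the protocol, Week 76 appears as the TSQM-9 time point for Part B (2.2.5 and 11.4.6).

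**What will be summarised.** SAP 9.6.5 provides for descriptive statistics by treatment group in the mITT. Its list ends at item 14, OFF hours in the "sub-population of subjects taking levodopa and three additional concomitant anti-PD medications". Protocol 11.4.5 lists all 16 items for the same kind of summary.

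**Compliance.** SAP 9.3.1: "Compliance will be summarized overall and by scheduled weeks (Week 2, 6, 18 and 24"). Protocol 11.5.2: "Compliance will be summarized overall and by week for each treatment group", with no week excluded.

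**TSQM-9 domains.** Protocol 7.7 says that the instrument "provides 4 domain scores: effectiveness, convenience, and global satisfaction". It announces four domains and names three.

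**The concern.** Tables are programmed from the SAP, and section 1 says that the shells were still to be developed. A programmer who follows the text would find a TSQM-9 time point outside the phase that the document covers, no entry for either questionnaire in the section that defines the exploratory summaries, and no Week 12 row for compliance.

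Two of the instruments that patients complete in Part A would then have no planned tabulation by randomised arm. Week 76 cannot stand in for Weeks 6 and 24. Under protocol 3.1, patients who had placebo in Part A start open-label tozadenant in Part B, so there is no concurrent placebo group at that visit.

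**Working it through.** The point depends on no power or alpha figure, so the check compares time points and lists.

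**1. TSQM-9 time point**
- Part A lasts 24 weeks and Part B lasts 52 weeks (SAP section 1).
- End of treatment in Part B: 24 + 52 = Week 76.
- Distance of the SAP's TSQM-9 time point from the end of Part A: 76 − 24 = 52 weeks.
- SAP Table 3-1 marks TSQM-9 at Visit 4 (Week 6), Visit 7 (Week 24) and Early Termination. It marks nothing at Baseline.

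SAP 4.2.3 therefore conflicts with the SAP's own schedule as well as with the protocol.

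**2. Declared against summarised endpoints**

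| Source | Items | EQ-5D-5L | TSQM-9 |
|---|---|---|---|
| Protocol 2.2.4 | 16 | item 15 | item 16, Weeks 6 and 24 |
| Protocol 11.2.1.4 | 14 | absent | absent |
| Protocol 11.4.5 | 16 | item 15 | item 16, Weeks 6 and 24 |
| SAP 4.2.3 | 16 | item 15 | item 16, Week 76 |
| SAP 9.6.5 | 14 | absent | absent |

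Missing from SAP 9.6.5: 16 − 14 = 2, namely items 15 and 16. Protocol 11.2.1.4 has the same gap. EQ-5D-5L is collected at Baseline, Week 24 and Early Termination (SAP Table 3-1), so a change to Week 24 can be computed. The SAP gives missing-item rules for PDQ-39 (9.6.4), ESS (9.7.7) and mMIDI (9.7.9), but none for these two instruments.

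**3. Compliance visits**
- Scheduled Part A visits after Baseline: Weeks 2, 6, 12, 18 and 24, five in all (SAP section 3).
- Weeks named in SAP 9.3.1: 2, 6, 18 and 24, four in all.
- Missing: Week 12.

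At the Week 12 visit the kit dispensed at Week 6 is collected and compliance is documented (protocol 6.2.12). The data for that row exist, and the SAP gives no reason for leaving it out.

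**The case against.** The best case on the other side is that these are drafting slips that would correct themselves.

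- **Read with the protocol.** SAP section 1 asks to be read alongside the protocol, and protocol 11.4.5 calls for both questionnaires. SAP 4.2.3 gives EQ-5D-5L a change to Week 24, and SAP 3.1.3 assigns all efficacy summaries to the mITT. The list in 9.6.5 is introduced as what the variables include, which leaves slight room to add to it. SAP section 8 allows exploratory analyses to be modified. This stands in part. A reader might infer that the results certainly would not be produced, and the documents do not go that far. But permission to correct is not a correction, and item 16 would still point to Week 76.
- **Descriptive only.** A reader might infer that a randomised comparison is lost. Protocol 11.4.5 and SAP 9.6.5 both say that no statistical analyses are planned for these variables, and the data are still collected at Weeks 6 and 24. What is missing is the instruction for a descriptive table, and that can be restored. This objection stands.
- **No real Week 76 output.** A reader might fear that an uncontrolled Week 76 result would be reported as a Part A finding. Week 76 belongs to Part B, which is to have its own SAP, and Part A is locked and unblinded when it completes. The wording matches the protocol's Part B item, so a copying slip is likely, though the documents do not say so. This stands.
- **Compliance.** A reader might infer that dosing over Weeks 6 to 12, 6/24 = 25% of the treatment time, goes unreported. SAP 9.3.1 still summarises overall compliance, days of exposure, and tablets taken, returned and lost, and all of these cover that period. The 25% also assumes that each by-week figure covers only the interval since the previous visit, which neither document states. If the figures are cumulative, the Week 18 row already includes Weeks 6 to 12. Only the separate Week 12 row is missing.
- **Version mismatch.** The SAP was written against protocol Amendment No. 1, and the protocol in hand is Amendment No. 3. Part of the contrast between the two may reflect this. The conflict of SAP 4.2.3 with Table 3-1 and with 9.6.5 lies inside one document and does not depend on it.

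**Conclusion.** The point holds as a wording error in the operative plan, and it is minor. Followed as written, the SAP misplaces one Part A endpoint by 52 weeks, provides no summary entry for two of 16 declared exploratory endpoints, and omits one of five visits from the by-week compliance summary. No primary, key secondary, safety or type I error result is affected.

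The conclusion assumes that programmers take the 14 items in SAP 9.6.5 as the complete list, which is the natural reading because they repeat the first 14 items of 4.2.3 in order. It also takes the specific statement in 9.6.5 that these variables are descriptive over the general mention of exploratory analyses in SAP 4.5, where a repeated-measures model with a baseline covariate is described. TSQM-9 has no scheduled baseline value for such a model.

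The domain count in protocol 7.7 is clerical and adds nothing to the size of the point.

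**What to change.** 1. **SAP 4.2.3, item 16:** change the time point to Weeks 6 and 24. Specify observed scores, because no baseline TSQM-9 is scheduled.
2. **SAP 9.6.5:** add EQ-5D-5L (change from Baseline to Week 24) as item 15 and TSQM-9 (Weeks 6 and 24) as item 16. State a scoring rule and a missing-item rule for each, since the new tables cannot be programmed without them.
3. **Protocol 11.2.1.4:** add the same two items, so that it agrees with 2.2.4 and 11.4.5.
4. **SAP 9.3.1:** add Week 12. It would help to say whether by-week compliance is per interval or cumulative.
5. **Protocol 7.7:** make the number of TSQM-9 domains agree with the three that are named.

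The cost is text edits and a few small descriptive tables from data already collected. No new assessment or visit is needed. The edits should be made before Part A is unblinded, so that no one can later ask whether the TSQM-9 time point was chosen after the data were seen.
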